Population:	
Aim 1: Patients ≥ 65 years admitted to one of the study inpatient units
 
Aim 2a: Any patient ≥ 18 years admitted to one of the study inpatient units with ADRD/delirium
 
Aim 2b: Adult Caregiver of any patient in aim 2a

Intervention:	Palliative Care Educator using video decision aid shown at time of admission to patients/caregivers in wards/units randomized to the intervention phase
Objectives:	The overall objective of the present proposal is to reduce the burden of COVID-19 and advanced illness and its consequences for an aging U.S. population.
Design/Methodology:	This project is a multi-center stepped wedge cluster randomized trial of an advance care planning (ACP) video intervention (vs. standard of care) using a Palliative Care Educator among patients ≥ 65 years OR any patient ≥ 18 years old with ADRD regardless of age admitted to one of the study inpatient units
Total Study Duration:	2 years
Subject Participation Duration:	EHR data collection during the 16 months of enrollment (2 months baseline plus 14 months intervention steps). EHR data abstracted for one year after the end of the 16 months of enrollment.

3 Background/Rationale & Purpose

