4.1 Study Objectives

The **overall objective** of this study is to reduce the burden of COVID-19 by expanding the reach of inpatient palliative care services, especially for patients with ADRD/Delirium. We propose to conduct a stepped wedge cluster randomized trial (SW-CRT) of a PCE video intervention among hospitalized patients aged 65 and over, or any patient ≥ 18 years with ADRD/Delirium and their caregivers in the ward and ICU settings of two major hospitals: Boston Medical Center (BMC) and North Shore University Hospital. Patient outcomes will be abstracted from electronic health records with Natural Language Processing (NLP).

We will test our hypotheses via the following **Specific Aims**:

Aim 1: To test the effects of a PCE video intervention leveraging video decision aids on the quality of end-of-life care. We will conduct a SW-CRT to evaluate intervention effectiveness by comparing the following outcomes among 9,000 hospitalized patients: ACP documentation; preferences for resuscitation; palliative care consults; and, hospice use. **Hypotheses:** *A higher proportion of patients in the intervention phase (vs. control) will: (1) complete advance care plans (primary outcome), (2) have documented resuscitation preferences, (3) have palliative care consults, (4) enroll in hospice over the course of one year of follow-up, and (5) have documented health care proxies.*

Aim 2a: The manual chart review activity is intended only for the patients whose caregiver participated in the survey activity. It is distinctive from the NLP activities described in our protocol which identify ACP documentation from the free-text of clinical notes. The chart review will involve a thorough human review of structured ACP elements such as DNR/DNI order, MOLST/POLST and Health Care Proxy form completion in each patient's chart.

Aim 2b: To characterize caregiver-centered outcomes of patients with ADRD/Delirium, including: (1) knowledge, (2) confidence in future care, (3) communication satisfaction, (4) decisional satisfaction, and (5) decisional conflict in 600 caregivers of patients with ADRD/Delirium admitted to the hospital. **Hypothesis:** *Intervention phase caregivers of patients with ADRD/Delirium (vs. control) will have higher knowledge, confidence, communication satisfaction, decisional satisfaction, and lower decisional conflict.*

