For Aim 2b, 600 caregivers of patients with ADRD/Delirium (300 control phase; 300 intervention phase) will be surveyed by telephone during (or within one week of) the index hospitalization to assess caregiver-centered outcomes.

Each day PCEs, who will be nurses or social workers on the palliative care team, will approach patients who are currently hospitalized under Aim 1 or Aim 2a. The PCE will then proactively use the goals-of-care video decision aid (or any of the additional videos regarding CPR, hospice, dementia, etc., as relevant and in the appropriate language) to provide educational support and assist in delivering primary palliative care services relating to goals-of-care conversations and ACP documentation. The videos range from 4-6 minutes in length and the PCE will watch the videos together with the patient and caregiver on an iPad (or remotely via telehealth with the caregiver).(130)

The PCE will arrange all video showings to include patient and caregiver (when possible and acceptable to the patient); when patients are unable to view a video (e.g., loss of capacity, delirium), the caregiver will view the video. The videos do not replace clinician counseling; indeed, they are designed to allow the PCE to confirm comprehension and to stimulate

conversation with a shared vocabulary. The PCE will then communicate the patient's or caregiver's wishes to the treating primary medical team to coordinate care.

In cases when the PCE deems that engagement with the full palliative care team is warranted, they will approach the treating primary medical team to place the consult. If/when the PCE exhausts the automated list for patients, they will coordinate with the palliative care consult team to select patients from the list of requested consultations. The PCE role will be fully integrated into existing hospital practices at our sites consistent with the pragmatic nature of this study design.

For Aim 1, the study population will consist of patients 65 years or older who are admitted to one of the study inpatient units in the hospital. For Aim 2a, the study population will consist of any patient ≥ 18 years admitted to one of the study inpatient units in the hospital with a diagnosis of ADRD/Delirium. For Aim 2b, the study population will consist of adult (≥ 18) caregivers of patients identified in Aim 2a. These caregivers will be recruited to complete a phone survey for our secondary caregiver outcomes

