7.1 Subject Inclusion Criteria

Over the two years of the trial, we will examine data on approximately 15,000 patients ≥ 65 admitted to these 23* units for our primary and secondary outcomes (Aim 1). Given the pragmatic nature of this trial, our inclusion criteria are quite broad and consistent with the goal of pragmatic trials.

We will also survey caregivers of 600 patients with ADRD/Delirium to conduct a telephone administered survey for caregiver-centered outcomes (knowledge, confidence, communication satisfaction, decisional satisfaction, and decisional conflict) during the index hospitalization. Caregivers may or may not be designated as ADRD/Delirium legal surrogate decision maker for the patient (i.e., most patients with ADRD/Delirium do not have a legally designated representative.) Any adult identified in the EHR as the contact family member or friend will be eligible to partake in the caregiver survey. Half of surveys will be conducted during the control period; half during the intervention period. Caregivers will be either English- or Spanish-speaking adults, which are the languages in which our surveys are validated. For patients in the control group, surveys will be completed during the hospital stay or within 1 week of discharge. For patients in the intervention group, the survey will be completed AFTER the PCE intervention, and up to 1 week after discharge.

*14 units (7 per hospital) will be included in the stepped wedge trial, an additional 9 units (3 at BMC and 6 at NorthShore) will be used to recruit additional control participants only. These additional units were added due to low recruitment at the start of the study and the decreasing number of control units as the stepped wedge design progresses. The target enrollment of 600 caregivers is still accurate.

Adding delirium to the list of eligible diagnoses will also increase the potential number of eligible subjects. The surveys are applicable to the caregiver of any patient who is not capable of making their own health decisions; this includes patients who are experiencing any sort of memory or cognitive decline.

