Aim 2b: Study staff will contact identified adult caregivers by phone to describe the survey activity

Recruitment

For Aim 1, all patients over the age of 65 will be included in the trial. For those patients admitted to wards/units in the intervention phase, the PCE will proceed with primary palliative care and view the ACP videos with the patients and family. For patients over the age of 65 admitted to wards/units that are in the control phase, usual care will proceed without the use of the PCE.

For Aim 2a, we will identify 600 inpatients to the study units with ADRD/Delirium who are 18+ years old.

For Aim 2b, 300 caregivers of the patients identified in Aim 2a will be surveyed during the control phase, and 300 caregivers will be surveyed during the intervention phase. For the group of caregivers (N=600) being surveyed for caregiver-centered outcomes, individual verbal informed consent will be obtained. The RA will survey caregivers using a validated survey tool. For patients with ADRD/Delirium and their caregivers that are admitted to a ward/unit that has been randomized to the intervention, the PCE will proceed with the video intervention.

Recruitment efforts for the caregiver survey (Aim 2) will be limited to English- and Spanish-speaking caregivers who are able to independently consent to participate in a research study. Research staff will work with the care team on the inpatient units where identified patients are currently hospitalized. The health care team will locate (either in person or by phone) designated caregivers for identified patients and invite them to participate. A member of the care

team will approach the caregiver and ask if they would be interested in getting a phone call from the research team to get more information about the study. If the caregiver says yes, the RA will call them, read the recruitment script (attached), and, if the subject is willing, review the consent form and complete the survey. If the designated caregiver cannot be located to invite to participate, an invitation letter with opt-out postcard will be mailed to them.

Informed Consent

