Every 2 months (the size of each step; 1 baseline + 7 steps = 8 data transfers) the outcomes of interest using NLP will be transferred to our data collection site (DFCI). Data on the following outcomes will be collected until the end of the study period.

- ACP discussion (e.g., goals-of-care discussion, advance directive, MOLST/POLST, code status, etc.)
- Resuscitation preferences
- Palliative care consults
- Hospice Use
- Health care proxy discussion

As stated above, direct identifiers will be held at each respective site (BMC researchers can see BMC identifiers but not North Shore University Hospital's identifiers, and vice versa.) The risks will be minimal as the data will be stored and analyzed on a HIPAA secure cluster at each site. None of the data will be stored in paper form. The data and identifiers will be kept for seven years after the end of the study period on the HIPAA secure cluster computer at each site. After the seven years, all HIPAA identifiers and all linking codes will be permanently destroyed in accordance with regulation.

NLP Validation

Prior to the use of NLP for outcome assessment in this trial, we will entrain and validate the NLP process for each of our two study sites. Specifically, we will use historic note data from a sample of 20 patients from each site who meet enrollment criteria. We will then measure the validity of this process by comparing results from human assisted NLP to a human chart review. The goal of the keyword library validation process is to ensure that the keyword library and abstraction guidelines accurately represent the language used to communicate information associated study outcomes. The semi-automated note annotation process will be cross-validated across both sites. Clinical notes will be the substrate of this process and must be requested from each site's clinical data warehouse.

Each site will ensure that the appropriate IRB and Data Sharing protocols are in place before this activity begins.

Chart Review

EHR data will be extracted by manual chart review on all Aim 2a patients whose caregiver completes a survey (2b). This survey will be limited to the inpatient stay that generated the survey, and include the following elements for collection of secondary outcomes:

- DNR/DNI order
- MOLST/POLST filed
- Resuscitation/Intubation preferences
- Health Care Proxy specified
- Palliative Care Consult during hospitalization

- Discharge Disposition

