We will conduct analyses related to potential effect modification as a step in our model validation process and to identify relationships that can be examined more fully in future research. Should interactions not be found to be statistically significant, we will fit a main effects-only model and use it to formally evaluate confounding by applying a change-in-estimates approach, with a 10% change in estimates being an initial screening criterion. **Secondary outcomes:** Similar procedures will be undertaken to assess intervention effects for the other EHR derived outcomes (documented orders for resuscitation preferences, palliative care consults, hospice enrollment, and documented health care proxies).

For our primary analysis, we will consider our primary outcome (ACP documentation) and our secondary outcomes (resuscitation preferences, palliative care, hospice use, and health care proxies) only for the patient's index hospitalization. However, because we expect some patients to have multiple rehospitalizations during the same step and may also include intervention time (i.e., crossover design), we will perform secondary analyses on all of our primary and secondary outcomes for each patient reviewing all EHR records from the index hospitalization of the patient until their death (or through study period). We will also perform stratified sensitivity analyses of patients who contribute only to control period vs. patients who contribute only to intervention period vs. those that contribute to both control and intervention periods.

We will conduct the above analyses on all Aim 1 and Aim 2a patients for the study primary and secondary outcomes.

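### Section 12.3 analyses all Aim 2a patients, but Aim 2a has two incompatible meanings, and under one of them the phase comparison is conditional on contact with the educator

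*Combined protocol and SAP*

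**What the plan says.** Section 12.3 (Statistical Methods, Aim 1) closes its account of the models for the primary and secondary outcomes with: "We will conduct the above analyses on all Aim 1 and Aim 2a patients for the study primary and secondary outcomes". It does not say which Aim 2a patients, or which data source supplies their outcome. The same section commits to intent-to-treat comparisons.

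**Text that makes Aim 2a broad**
- Synopsis, Population: "Aim 2a: Any patient ≥ 18 years admitted to one of the study inpatient units with ADRD/delirium".
- Section 5, Study Design: "For Aim 2a, the study population will consist of any patient ≥ 18 years admitted to one of the study inpatient units", with a diagnosis of ADRD/delirium. Section 4.2.2 describes the group in the same way.
- Section 9, NLP Data Collection: Aim 1 and Aim 2a records together are about 15,000 patients.

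**Text that makes Aim 2a narrow**
- Section 4.1, under the Aim 2a label, describes only a chart review: "The manual chart review activity is intended only for the patients whose caregiver participated in the survey activity". It sets this apart from the NLP work.
- Section 9, Recruitment: "For Aim 2a, we will identify 600 inpatients to the study units with ADRD/Delirium who are 18+ years old". That is also the number of caregivers to be surveyed.
- Section 9, Chart Review: manual extraction covers Aim 2a patients with a completed caregiver survey, and its stated purpose is to supply secondary outcomes.
- Section 9, Informed Consent: the Aim 2a waiver is justified by calling the activity a chart review.

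**How surveyed patients enter.** Section 7.1 says that in the intervention group "the survey will be completed AFTER the PCE intervention, and up to 1 week after discharge". Control surveys may be done at any time in the stay or within a week of discharge. A footnote adds nine units, outside the 14 in the stepped wedge, that recruit controls only.

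**The concern.** The two meanings lead to different comparisons. The broad set is defined by diagnosis, age and unit, so classifying it by unit phase respects the randomisation. The chart-reviewed set depends on something that happens after the unit has crossed over: in the intervention phase, a patient whom the educator never reached cannot yield a survey that meets the timing rule. Control patients face no matching condition.

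The outcome makes this matter. The educator's task includes completing ACP documentation in the record (section 8), and any qualifying note on goals of care, code status, palliative care and similar topics counts (section 4.2.1). Restricting one phase to patients seen by the person who writes the documentation, and leaving the other unrestricted, departs from intent-to-treat in a direction that usually favours the intervention. Controls from the nine added units bring in a further comparison that randomisation does not protect.

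At stake is mainly the Aim 2a secondary outcome, ACP documentation in the record. A lesser matter is that section 12.3 can be read as pooling Aim 2a into the primary analysis, so that the age range and units of the primary set are not fixed.

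**Working it through.** No figure in the plan is in dispute. The check sets the texts against each other and then sizes the selection under stated assumptions.

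**1. Can the texts be reconciled?** Not fully. The broad reading fits the synopsis, sections 4.2.2 and 5 and the NLP text, but it leaves the count of 600 and the chart review as a source of secondary outcomes unexplained. The narrow reading explains those, but it contradicts a population of any eligible adult and the inclusion of Aim 2a in about 15,000 NLP records. No sentence settles which set section 12.3 means.

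**2. Entry conditions for the chart-reviewed set**

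| Condition | Intervention phase | Control phase |
|---|---|---|
| Caregiver located, speaks English or Spanish, consents | required | required |
| Educator intervention before the survey | required by the timing rule | no counterpart |
| Units | the 14 randomised | the 14 randomised plus 9 control-only |

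The first row applies to both phases. The second and third do not match.

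**3. A real effect, arising only in reached patients.** Let r be the share of eligible intervention-phase patients whom the educator reaches. The documents do not give r, so it is an assumption. Take the plan's benchmark of 25% to 35% (sections 12.2 and 12.3) as the true effect over all eligible patients, and assume that reached patients otherwise resemble controls. The difference in a set restricted to reached patients is 10 / r:
- r = 0.9: 10 / 0.9 = 11.1 points
- r = 0.7: 10 / 0.7 = 14.3 points
- r = 0.5: 10 / 0.5 = 20 points
- r = 0.3: 10 / 0.3 = 33.3 points

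**4. No effect, but reached patients are more likely to have documentation anyway.** Let p_r and p_u be the rates in reached and unreached patients, with r·p_r + (1 − r)·p_u = 0.25 and an odds ratio of 1.5 to 2.0 between them (assumed). The spurious difference is p_r − 0.25. Example: r = 0.5 and odds ratio 2.0 give p_r = 0.314 and p_u = 0.186, a difference of 6.4 points. For the type I error, take 300 per phase and borrow the design effect of 2.03 that section 12.2 gives for the 600-subject sample, so the effective n is 300 / 2.03 = 147.8 per phase. In the example the standard error is √[(0.314 × 0.686 + 0.25 × 0.75) / 147.8] = 0.052, and the two-sided error is about 23%.

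| Reach | Spurious difference (points) | Two-sided type I error |
|---|---|---|
| 90% | 0.7 to 1.1 | 5.2% to 5.5% |
| 70% | 2.2 to 3.6 | 7.1% to 10.7% |
| 50% | 3.8 to 6.4 | 11.3% to 23.1% |
| 30% | 5.5 to 9.6 | 18.5% to 44.0% |

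If reached patients were less likely to have documentation, the sign would reverse.

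**5. Effect on a pooled primary result.** Patients aged 65 or over with ADRD/delirium on the 14 units are in Aim 1 already, reached or not. In the intervention phase, pooling the narrow set therefore adds only surveyed patients under 65. Assume these are 10% to 50% of 300, that is 30 to 150. Seven clusters over eight periods give 28 control and 28 intervention cluster-periods, so with equal enrolment about 7,500 of 15,000 patients fall in each phase.
- Benchmark effect at 50% reach: reached patients at 25 + 20 = 45%, all patients at 35%, a gap of 10 points. Shift: 30 × 10 / 7,530 = 0.04 to 150 × 10 / 7,650 = 0.2 points.
- Extreme case, 20% reach with every reached patient documented: all patients at 25 + 0.75 × 20 = 40%, reached at 100%, a gap of 60. Shift: 30 × 60 / 7,530 = 0.2 to 150 × 60 / 7,650 = 1.2 points.
- Section 4.1 gives 9,000 patients instead of 15,000. With 4,500 per phase the extreme case becomes 30 × 60 / 4,530 = 0.4 to 150 × 60 / 4,650 = 1.9 points.

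This step covers selection on educator contact only, not any use of the nine added units in Aim 1.

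**The case against.** The best defence is that the plan already means the broad set. Every sentence that defines the Aim 2a population is broad. Section 4.1 restricts an activity, the chart review, and the chart review text in section 9 treats surveyed patients as a subset of Aim 2a. Section 12.3 says all. On that reading there is no selection on educator contact. This largely stands: the broad reading is available and sound. It does not dispose of the count of 600, or of the statement that the chart review supplies secondary outcomes. An analyst could follow either text.

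Second, the rule in section 7.1 is about timing and is not written as an eligibility criterion, and section 5 plans for every eligible patient on an intervention-phase unit to receive the intervention. At near-complete reach little is lost, as the 90% rows show. That is fair, but complete reach is a plan and not a given: section 5 speaks of what happens if or when the educator exhausts the daily list.

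Third, control patients are selected too, through caregiver location, language and consent. True, but those filters act in both phases and do not offset the one that acts in one.

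Fourth, the synopsis describes the design as covering patients of 65 or over or adults with ADRD of any age, and section 4.2.1 sets no age limit for the primary outcome. A reader might infer that including patients under 65 in the primary analysis is an error. The documents do not support that. They leave the set unstated, and either choice can be defended.

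**Conclusion.** The point holds as an unresolved conflict over an analysis set, and it should be settled before analysis. If the chart-reviewed patients are compared by phase for ACP documentation, the result is not intent-to-treat, tends to favour the intervention, and includes some controls from outside the stepped wedge. A true 10-point effect would appear as about 11, 14 or 20 points at 90%, 70% or 50% reach, assuming that the effect arises only in reached patients and that they otherwise resemble controls.

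Three stronger conclusions are tempting, and the documents do not support them. They do not show that the plan will use the selected set. They do not support an apparent effect near 75 points (100% against 25%), which needs low reach together with documentation in every reached patient; neither figure is in the plan, and section 5 intends full reach. Nor do they show material bias in the primary outcome: the pooled shift is at most a point or two even at those extreme rates, and a fraction of a point at the plan's benchmark effect.

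**What to change.** In section 12.3:
- Define the Aim 2a comparison as all eligible ADRD/delirium inpatients aged 18 or over on the 14 randomised units, classified by unit phase whether or not the educator was seen, with NLP as the outcome source.
- Keep the chart review of surveyed patients, including items that are not in the NLP list, such as discharge disposition. Report it as descriptive or validation data and not as a randomised phase comparison.
- State whether the primary analysis set is Aim 1 (65 or over) alone or also includes younger ADRD/delirium patients, and limit it to the 14 randomised units.

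Then align sections 4.1 and 9, so that the 600 refers to the surveyed and chart-reviewed subset and not to Aim 2a as a whole.

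No new data collection is needed, because NLP extraction is already planned for both aims. The costs are that the Aim 2a effect may look smaller, and that items found only in the chart review lose a formal comparison by phase.
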